2 SUBJECT POPULATIONS (ANALYSIS SETS)

2.1 Efficacy

2.1.1 Intention-To-Treat population (ITT)

The ITT population is:

All randomised subjects who received even a partial dose of study drug.

Subjects will be assessed according to their randomised treatment, regardless of the treatment they receive.

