3.2.1.1 Primary efficacy analyses

The primary endpoint of treatment success will be tested sequentially (hierarchical structure) with the first test being non-inferiority test based upon the treatment difference. A rejection of the null hypothesis will trigger superiority testing.

The two hypothesis tests are hierarchically structured so that the second test (superiority) will only be considered if the first test (non-inferiority) is accepted. The superiority test is powered

to detect an absolute difference of 18 %. There is no alpha adjustment for the second test as a result of the hierarchical testing.

The primary efficacy analysis will be based on the mITT population and repeated on the PP population in order to assess the robustness of the results.

The primary efficacy variable is the proportion of subjects with successful overall preparation evaluated with the scale (from 1 to 4) of the Cleansing Score as assessed by the colonoscopist.

A successful preparation will be defined as excellent (4) or good (3) preparation.

A failure preparation will be defined as:

- Fair (2) or poor (1) according to colon cleansing score,
- Any subject who did not have a colonoscopy based on the investigator's assessment of the cleansing (insufficient faecal output, unclear faecal discharge, etc.) or due to preparation related AEs,
- Any subject for whom cleaning was not adequate for evaluation,
- Any subject for whom rescue treatment (saline enema) was needed.

The proportion of subjects with successful colon cleansing (graded as excellent or good) will be summarised along with the 95 % CI using the standard Wald asymptotic CI using the following SAS code:

```
proc freq data=ADCC(where=(PARAM='Successful overall preparation' and MITTFL='Y'));
```

```
table AVALC / missing binomial(level='Yes' cl=wald);
```

by TRTP;

run;

The primary efficacy endpoint will be analysed using a logistic regression model including treatment and country as covariates as well as the interaction between treatment and country if it is significant (i.e. p < 0.10, as interaction tests have low power) using the following SAS code providing the adjusted proportions with their 95 % CI thank to ilink option, and with the option firth in the model with interaction since there might otherwise be a quasi-complete separation of data points affecting the validity of the model:

proc logistic data=ADCC(where=(PARAM='Successful overall preparation' and MITTFL='Y'));

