3.2.1.2.2 Overall and segmental cleansing scores assessed by BBPS

The overall (LC + TC + RC) and segmental (LC, TC, RC) cleansing scores will be assessed by BBPS (see Table 3) and will be presented by treatment group using descriptive summary statistics (mean, SD, median, quartiles and ranges) and using a two-way analysis of variance (ANOVA) including treatment and country as well as the interaction between treatment and country, if it is significant (i.e. p < 0.10), as covariates using the following SAS code:

proc mixed data=ADCC(where=(PARAM='BBPS - Global Score'/'BBPS - Left colon score'/'BBPS - Transverse colon score'/'BBPS - Right colon score' and ITTFL='Y')); class TRTP COUNTRYC; model AVAL = TRTP COUNTRYC TRTP*COUNTRYC;

```
lsmeans TRTP / diff cl;
```

run;

30/62

The adjusted mean scores, the adjusted treatment differences with their 95 % CI and the p-value of difference will be summarised.

In addition, this analysis will also be produced per country so that mean scores and the estimated treatment differences will also be provided per country using the following SAS code.

proc mixed data=ADCC(where=(PARAM='BBPS - Global Score'/'BBPS - Left colon score'/'BBPS - Transverse colon score'/'BBPS - Right colon score' and ITTFL='Y')); class TRTP COUNTRYC; model AVAL = TRTP COUNTRYC TRTP*COUNTRYC; lsmeans TRTP*COUNTRYC / diff cl;

run;

The proportion of subjects with successful overall preparation, assessed by the total score of the BBPS, will also be presented. Successful overall preparation will be defined based on a global BBPS score ≥ 6 for the sum of the 3 segments (right, transverse and left colon) and will be presented by treatment group using frequency count with two-sided 95 % CI and analysed using Cochran-Mantel-Hænszel (CMH) chi-square for the proportions adjusting for country effect. The general association statistic will be used to assess the test significance.

The SAS Freq procedure will be used as follows:

```
proc freq data= ADCC(where=(PARAM='Successful overall preparation BBPS' and ITTFL='Y'));
```

table COUNTRYC*TRTP*AVALC / CMH;

run;

The difference of proportions with the 95 % CI and p-value will be summarised.

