3.2.3 Missing data and outliers

3.2.3.1 Missing data

No missing value will be replaced, except for the primary analysis where the missing preparation evaluations (because of colonoscopy not done because of inadequate preparation or preparation-related AEs) will be considered as failures.

In the description of qualitative parameters, subjects with a value counted as "missing" at a visit will be identified as subjects being not assessed.

If a value required a retest, the last reliable non-missing value will be taken into account if measured before the first intake of treatment; and the first non-missing reliable value for postbaseline assessments. An assessment will be considered reliable if it is performed without any technical problem and if the result is within the range of plausible values. Any retest or unscheduled assessments performed will be included in the individual subject data listings.

If there is a significant number of missing values for a subject (or if there is confirmed data appearing spurious), a decision will be made following consultation with the sponsor regarding the handling of these data in summaries, prior to database freeze.

Any repeat or additional assessments performed will be included in the individual subject data listings.

3.2.3.2 *Missing or incomplete dates*

In all listings, missing or incomplete dates should be left as they have been recorded. However, for calculation / sorting / assignation based on dates, the following methods will be used:

- The most conservative approach will be systematically considered (i.e. if the onset date of an AE/concomitant medication is missing / incomplete, it is assumed to have occurred during the study treatment phase (i.e. a TEAE for AEs) except if the partial onset date or other data [stop date, ...] indicates differently).
- A missing/incomplete date of medical history or disease diagnosis will be assumed to have occurred before any study treatment.
- If a partial date and the associated information do not allow to state about the assignation to a group / category, all the possible groups / categories will be considered (e.g. a medication with partial start and stop dates could be considered as prior and concomitant treatment).

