3.2.11 Rules and data formats

Data will be presented using an appropriate number of decimal places (i.e. the number of decimal places used does not imply undue precision). Raw data will be presented to the number of decimal places collected, and derived data will be presented to an appropriate number of decimal places. The appropriate number of decimal places will be determined by general practice, mathematical rationale or scientific rationale (e.g. age should be presented in whole numbers).

For summary statistics, the following will be presented n, arithmetic mean, SD, median and the range (minimum, maximum).

Mean, SD and median values will be reported to one decimal place greater than the raw/derived data that they summarise. Minimum and maximum values will be reported with the same precision as the raw data.

Percentages will be reported to 1 decimal place and 0 % will not be presented. Percentages will be calculated using a denominator of all subjects in a specified population with available data. The denominator will be specified in a footnote to the tables for clarification if necessary.

All values below or above a limit of detection (e.g. < 0.1 or > 100) will be listed as such. For each parameter for which it is possible to have values below or above a limit of quantification, the rule to be used in the statistical tables is to replace values below or above a limit of quantification by the limit of quantification.

All text fields must be left justified and numeric or numeric with some text specification (e.g. not done, unknown, < 4.5, ...) must be decimal justified. Dates will be presented in the format [ddmmmyyyy] and times in the format [hh:mm].

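### The descriptive BBPS success rate leaves out subjects not scoped because preparation failed, and counts enema-rescued subjects who then score 6 or more as successes

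*SAP*

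**What the plan says.** SAP 3.2.1.2.2 analyses the BBPS total and segment scores as means. It then adds a proportion: "Successful overall preparation will be defined based on a global BBPS score ≥ 6 for the sum of the 3 segments". That proportion is reported by arm with a confidence interval, a difference and a p-value. The test is a country-stratified CMH on ITT-flagged records ("table COUNTRYC*TRTP*AVALC / CMH").

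ITT is defined in SAP 2.1.1 as "All randomised subjects who received even a partial dose of study drug", so it includes treated subjects who never had a colonoscopy.

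Two general rules decide what happens to a subject without a score:
- SAP 3.2.3.1: "No missing value will be replaced, except for the primary analysis". The exception that follows covers colonoscopies not done because of inadequate preparation or preparation-related adverse events, and it is confined to the primary analysis.
- SAP 3.2.11: percentages use a "denominator of all subjects in a specified population with available data".

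For the primary endpoint, SAP 3.2.1.1 and Appendix 1 item 3 list the failures. They include subjects not scoped for those reasons and "Any subject for whom rescue treatment (saline enema) was needed". Appendix 1 has no derivation for BBPS success. Protocol 3.4 and 6.1.3 place the rescue enema before the procedure, so BBPS is scored after any enema.

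**The concern.** Two groups of clear preparation failures are handled differently by two success rates in the same report. A subject whose preparation was too poor for colonoscopy is a failure on the primary endpoint but is absent from the BBPS rate, although that analysis is labelled ITT. A subject who needed an enema is a primary failure but a BBPS success if the cleaned colon scores 6 or more.

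Both departures raise the BBPS rate. If one preparation cleanses less well and so produces more cancellations or enemas, its rate is raised more, and the BBPS comparison moves towards no difference. The rate bears on the first secondary objective (SAP 1.2.2, overall and segmental cleansing) and carries a confidence interval and p-value, so it is likely to be read beside the primary result.

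**Working it through.** **The plan's own figure.** The documents state no expected BBPS success rate. The only related figure is the primary sample size (Protocol 10.2): 85% success in both arms, margin 15%, one-sided alpha 0.025, power 90%. By the unpooled normal approximation, n = (1.960 + 1.282)² × 2 × 0.85 × 0.15 / 0.15² ≈ 119.1, rounded up to 120 per arm; 120 / 0.96 = 125. Both figures reproduce, and neither depends on the BBPS definition.

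**Handling of each group.**

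| Subject | Primary endpoint | BBPS success as written |
|---|---|---|
| Not scoped, preparation inadequate or preparation-related AE | Failure (stated) | No score, so out of numerator and denominator (SAP 3.2.3.1 with 3.2.11) |
| Enema given, BBPS 6 or more afterwards | Failure (stated) | Success (no rescue clause) |
| Enema given, BBPS below 6 | Failure | Failure |

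The first row follows from stated rules. The second follows from the absence of a clause.

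**Size in one arm.** Assumptions, none of them from the documents except N:
- N = 125 treated (all those randomised to the arm)
- f = 10 other failures, failing under either rule
- c = 0 to 8 cancelled for poor preparation
- e = 0 to 15 rescued, all scoring 6 or more

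Formulas:
- With the primary failure rules: (N − c − e − f) / N
- BBPS as written: (N − c − f) / (N − c), which does not depend on e

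| c | e | Primary failure rules | BBPS as written | Inflation (points) |
|---|---|---|---|---|
| 0 | 0 | 115/125 = 92.0% | 115/125 = 92.0% | 0.0 |
| 2 | 5 | 108/125 = 86.4% | 113/123 = 91.9% | 5.5 |
| 5 | 5 | 105/125 = 84.0% | 110/120 = 91.7% | 7.7 |
| 5 | 10 | 100/125 = 80.0% | 110/120 = 91.7% | 11.7 |
| 8 | 0 | 107/125 = 85.6% | 107/117 = 91.5% | 5.9 |
| 0 | 15 | 100/125 = 80.0% | 115/125 = 92.0% | 12.0 |
| 8 | 15 | 92/125 = 73.6% | 107/117 = 91.5% | 17.9 |

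Cancellations alone add at most 5.9 points in this range, and rescues alone at most 12.0. The largest value goes with a 73.6% success rate, well under the 85% planned for the primary endpoint. The rows nearest 85% show about 5 to 8 points.

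**Effect on the treatment difference** (f = 10 in each arm).

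| Eziclen/Izinova (c, e) | Klean-Prep (c, e) | Primary failure rules | BBPS as written |
|---|---|---|---|
| 2, 3 | 5, 10 | 88.0% vs 80.0%, +8.0 | 91.9% vs 91.7%, +0.2 |
| 5, 10 | 2, 3 | 80.0% vs 88.0%, −8.0 | 91.7% vs 91.9%, −0.2 |
| 5, 5 | 5, 5 | 84.0% vs 84.0%, 0.0 | 91.7% vs 91.7%, 0.0 |

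The distortion can run in either direction and vanishes when the counts match. If c and e match but f differs, the BBPS difference is only rescaled by N / (N − c), at most 125/117 ≈ 1.07 here.

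**The case against.** The strongest reply is that an as-observed BBPS rate is a legitimate secondary description. The scale grades mucosa seen at colonoscopy, so a subject not scoped has no grade. Adding the primary's failure components would also make the two endpoints agree partly by construction. This stands as a reason to keep the as-observed rate. It does not support presenting that rate as an ITT result without saying who is missing.

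A second reply is that neither group disappears from the report. Rescue use is its own ITT endpoint by arm (SAP 3.2.1.2.7), colonoscopies performed are tabulated by arm (SAP 3.2.5), and missing values are counted (SAP 3.2). This helps a careful reader but corrects neither the rate nor its p-value.

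Three stronger readings are tempting and are not supported:
- A reader might infer that the SAP adopts a rule making rescued subjects successes. It does not; it is silent, and only those who score 6 or more after the enema are affected.
- A reader might infer that the two endpoints share one label and that BBPS is meant to confirm the primary result. The SAP names the BBPS parameter separately. It assigns robustness to the PP repeat, the identity-link model and the bootstrap (SAP 3.2.1.1), and tests secondary endpoints descriptively (SAP 3.1.5).
- A reader might infer that a real difference of several points will be masked. That needs unequal counts, about which the documents say nothing.

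The table templates are in a separate document and the table list is redacted, so a clarifying footnote cannot be ruled out. SAP 3.2.11 provides for denominator footnotes only where necessary.

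**Conclusion.** The point holds as a small, inexpensive improvement to a descriptive secondary endpoint. The exclusion of subjects not scoped because preparation failed follows from the SAP's explicit missing-data and denominator rules. The success status of rescued subjects scoring 6 or more follows from the definition having no rescue clause. Repeating the analysis on mITT or PP, which happens only if those sets differ from ITT by more than 10%, would not extend the failure rules to BBPS.

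Under the assumed counts the rate is inflated by 0 to about 18 points. The treatment difference is distorted only if the counts differ between arms. These figures are illustrations, not estimates. The primary non-inferiority conclusion, its alpha and the sample size are unaffected.

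**What to change.** In SAP 3.2.1.2.2, with a matching item in Appendix 1, define BBPS success as a total score of at least 6 with no rescue enema. In this analysis, count ITT subjects who had no colonoscopy because the preparation was inadequate or caused adverse events as non-successes. Amend SAP 3.2.3.1 so that its exception also covers this analysis. Keep the as-observed rate as a supplementary row labelled as such, with its denominator shown, and leave the BBPS mean-score analyses unchanged.

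The cost is one sentence, one derivation line, one extra table row and a slightly lower reported BBPS rate. The change uses failure rules and data the trial already has, and it alters nothing in patient management.

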3.2.1.2.3 Time to clear effluent

The time to clear effluent as reported by the subject as the time between first intake of prescription and first clear watery stool will be assessed and will be analysed using survival methods.

Table 7 specifies the event and censoring dates to be used in the analysis of time to clear effluent.

Event	Time of event	Outcome
Clear watery stools	Time of clear watery stools	Event
No clear watery stools with colonoscopy	Time of colonoscope introduction	Censored
No clear watery stools without colonoscopy	Time of start of treatment + 12h	Censored

Table 7Time to Clear Effluent (hours)

The distribution of time to clear effluent will be estimated using the Kaplan-Meier (KM) product limit method. The results will be presented in a summary table and a KM plot will also be constructed.

The summary table will present by treatment group the numbers and percentages of subjects with occurrence of clear watery stool and the numbers and percentages of censored subjects. The summary will also include the median time to clear effluent as well as the 25th and 75th

31/62

percentiles with their two-sided 95 % CI, the percentage and 95 % CIs of subjects who had clear watery stool at 2, 3, 4, 5, 6, 9, 12, 15, 18 and 24 hours from KM estimates.

Confidence intervals for median time to clear effluent as well as the 25th and 75th percentile CIs will be calculated using the method of Brookmeyer and Crowley (1982) [5], which is the default method within SAS® version 9 and higher.

Kaplan-Meier curves will be constructed by treatment group and will display the number of subjects at risk at 1, 1.5, 2, 2.5, 3, 3.5, 6, 9, 12, 15, 18 and 24 hours.

In addition, the treatment difference will be tested using a Cox proportional hazards model adjusted on country and the association with treatment will be further explored by presenting separate KM plots for each country.

The SAS Phreg procedure will be used as follows:

Proc Phreg Data=ADTTE(where=(PARAMCD='Time to Clear Effluent (hours)' and ITTFL='Y'));

Class TRTP(ref='KLEAN-PREP') COUNTRYC(ref='Largest country'); Model AVAL*CNSR(1) = TRTP COUNTRYC / Ties = EXACT;

Run;

3.2.1.2.4 Complete procedure

The proportion of complete procedure (defined as procedures (i.e. colonoscopies) that reached the caecum) will be assessed. It will be tabulated by treatment group using frequency count with two-sided 95 % CI and analysed using Cochran-Mantel-Hænszel (CMH) chi-square for the proportions adjusting for country effect. The general association statistic will be used to assess the test significance.

The SAS Freq procedure will be used as follows:

proc freq data=ADPR(where=(PRTRT='COLONOSCOPY' and AVISITN=2 and ITTFL='Y'));

```
table COUNTRYC*TRTP*PROCCUR / CMH;
```

run;

The difference of proportions with the 95 % CI and p-value will be summarised.

The reasons for non-completion will also be presented.

3.2.1.2.5 *Time to caecal intubation*

The time to caecal intubation (from colonoscope introduction to caecal intubation) will be assessed and will be analysed using survival methods on subjects who performed colonoscopy.

Table 8 specifies the event and censoring dates to be used in the analysis of time to clear effluent.

	· · · · ·	
Event	Time of event	Outcome
Caecal intubation	Time of caecal intubation	Event
Procedure (i.e. colonoscopy) did not reach the caecum	Time of withdrawal of colonoscope	Censored

Table 8Time to caecal intubation (minutes)

The distribution of time to caecal intubation will be estimated using the Kaplan-Meier (KM) product limit method. The results will be presented in a summary table and a KM plot will also be constructed.

The summary table will present by treatment group the numbers and percentages of subjects with occurrence of caecal intubation and the numbers and percentages of censored subjects. The summary will also include the median time to caecal intubation as well as the 25th and 75th percentiles with their two-sided 95 % CI, the percentage and 95 % CIs of subjects who had caecal intubation at 5, 10, 15, 20, 25, 30, 45 and 60 minutes from KM estimates.

Confidence intervals for median time to caecal intubation as well as the 25th and 75th percentile CIs will be calculated using the method of Brookmeyer and Crowley (1982) [5], which is the default method within SAS® version 9 and higher.

Kaplan-Meier curves will be constructed by treatment group and will display the number of subjects at risk at 5, 10, 15, 20, 25, 30, 45 and 60 minutes.

In addition, the treatment difference will be tested using a Cox proportional hazards model adjusted on country and the association with treatment will be further explored by presenting separate KM plots for each country.

The SAS Phreg procedure will be used as follows:

Proc Phreg Data=ADTTE(where=(PARAMCD='Time to caecal intubation' and ITTFL='Y'));

Class TRTP(ref='KLEAN-PREP') COUNTRYC(ref='Largest country'); Model AVAL*CNSR(1) = TRTP COUNTRYC / Ties = EXACT;

Run;

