# 7.2 Secondary Efficacy Endpoints and Evaluations

Secondary efficacy endpoints and evaluations are summarised in Table 7.

**Table 7** Secondary Endpoints and Evaluations

Endpoint	Timepoint	Evaluation
Colon cleansing	Visit 2 (Colonoscopy)	Cleansing Score assessed on 4 levels (4-point scale (see Section 7.3.1)
Overall and segmental cleansing assessed by BBPS	Visit 2 (Colonoscopy)	BBPS (see Section 7.3.2.1) Overall score [14]. Segmental score (left colon (LC), transverse colon (TC), right colon (RC)).
Time to clear effluent	Treatment	Time between first intake of prescription and first clear watery stool.
Complete procedure	Visit 2 (Colonoscopy)	Number (%) of complete procedures defined as procedures that reached the caecum
Duration of intubation	Visit 2 (Colonoscopy)	Time between the colonoscope introduction and the time to reach caecum
Duration of examination	Visit 2 (Colonoscopy)	Duration of colonoscope withdrawal from caecum
Need for rescue treatment because of inadequate preparation intake.	Visit 2 (before colonoscopy)	Number (%) of procedures that need a rescue treatment (saline enema)
Treatment acceptability	Treatment	Level of acceptability of treatment assessed using a 5-point Treatment Acceptability Questionnaire (see Section 7.3.2.3).
Need for nasogastric tube	Treatment	Number (%) of subjects who need a nasogastric tube to complete preparation
Treatment compliance	Treatment	Volume of fluid not taken (see Section 7.3.2.2)

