3.2.1.2.7 Rescue treatment

The proportion of procedures that need a rescue treatment (saline enema) because of inadequate preparation intake will be assessed. It will be tabulated by treatment group using frequency count with two-sided 95 % CI and analysed using Cochran-Mantel-Hænszel (CMH) chi-square for the proportions adjusting for country effect. The general association statistic will be used to assess the test significance.

The SAS Freq procedure will be used as follows:

```
proc freq data=ADCM(where=(CMCAT='RESCUE MEDICATION' and CMTRT='ENEMA' and ITTFL='Y'));
table COUNTRYC*TRTP*CMOCCUR / CMH;
```

run;

The difference of proportions with the 95 % CI and p-value will be summarised.

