3.2.1.3.2 Wake-up during the night to have a bowel movement

The proportion of patients who wake-up during the night to have a bowel movement will also be tabulated by treatment group using frequency count with two-sided 95 % CI and analysed using Cochran-Mantel-Hænszel (CMH) chi-square for the proportions adjusting for country effect. The general association statistic will be used to assess the test significance.

The SAS Freq procedure will be used as follows:

proc freq data=ADCE(where=(CETERM='NIGHTLY BOWEL MOVEMENT' and ITTFL='Y'));

```
table COUNTRYC*TRTP*CEOCCUR / CMH;
```

run;

The difference of proportions with the 95 % CI and p-value will be summarised.

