Appendix 1 Derived data

The following derived data will be calculated:

(1) Treatment group

Treatment groups will be defined as "Eziclen/Izinova" and "Klean-Prep".

(2) Study duration

Study duration (days) will be calculated as (last visit attended - date of informed consent) + 1.

- (3) Successful treatment preparation
- A successful preparation will be derived from a colon cleansing scored as excellent (4) or good (3).
- A failure preparation will be defined as:
 - Fair (2) or poor (1) according to colon cleansing score,
 - Any subject who did not have a colonoscopy based on the investigator's assessment of the cleansing (insufficient faecal output, unclear faecal discharge, etc.) or due to preparation related AEs,
 - Any subject for whom cleaning was not adequate for evaluation,
 - Any subject for whom rescue treatment (saline enema) was needed.

(4) Time to clear effluent

It is defined as the time (expressed in hours) from the first intake of prescription to the first clear watery stool occurrence if any, or to the time of colonoscope introduction, if no clear watery stool is observed before the beginning of the procedure and then the time will be considered as censored for the survival analysis. See section 3.2.1.2.3.

(5) Completion of the procedure

"Yes" if the colonoscopy reached the caecum and the item "Was physician able to reach the caecum?" is "Yes", "No" otherwise.

(6) Duration of the intubation

It is defined as the time (expressed in minutes) from colonoscope introduction to caecal intubation.

(7) Duration of the examination

It is defined as the time (expressed in minutes) from caecal intubation to colonoscope withdrawal.

(8) Need of a rescue treatment

"Yes" if a rescue medication was administered and the item "Was any enema needed to achieve preparation?" is "Yes", "No" otherwise.

(9) Need of a nasogastric tube to complete preparation

"Yes" if a nasogastric tube was inserted and the item "Was a nasogastric tube inserted?" is "Yes" at dose 1 or dose 2, "No" otherwise.

(10) Compliance in percentage

The percentage of compliance is defined as (planned volume - residual volume) / planned volume, adding up the solution and water volume where applicable.

50/62

The planned volume is 750 mL for Eziclen (375 mL per dose), 1500 mL for hydration (750 mL per dose) and 70 mL/kg for Klean-Prep® with a maximum of 4000 mL (maximum 2000 mL per dose).

(11) Compliance with the instructions of use

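### The complete-procedure code in SAP 3.2.1.2.4 tabulates an undefined variable, PROCCUR, that most naturally means the colonoscopy took place, not that it reached the caecum

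*SAP*

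**What the plan says.** The written definition is consistent across both documents.

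- Protocol 7.2 (Table 7) gives the evaluation as "Number (%) of complete procedures defined as procedures that reached the caecum".
- SAP 3.2.1.2.4 says: "The proportion of complete procedure (defined as procedures (i.e. colonoscopies) that reached the caecum) will be assessed".
- SAP Appendix 1, item 5, sets completion to Yes "if the colonoscopy reached the caecum and the item" asking whether the physician could reach the caecum is answered Yes. Otherwise it is No.

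The code in SAP 3.2.1.2.4 selects the Visit 2 colonoscopy record in the ITT population, starting "proc freq data=ADPR(where=(PRTRT='COLONOSCOPY' and AVISITN=2 and ITTFL='Y", and then requests "table COUNTRYC*TRTP*PROCCUR / CMH". Neither line refers to the caecum item, and PROCCUR is not explained anywhere in the SAP.

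Two other sections use the same construction. Rescue treatment (SAP 3.2.1.2.7) selects the enema record, starting "proc freq data=ADCM(where=(CMCAT='RESCUE MEDICATION' and CMTRT='ENEMA' and ITTFL='Y", and requests "table COUNTRYC*TRTP*CMOCCUR / CMH". Night waking (SAP 3.2.1.3.2) selects the nightly bowel movement record and requests "table COUNTRYC*TRTP*CEOCCUR / CMH".

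**The concern.** In the two parallel uses, the variable ending in OCCUR says whether the thing named on the selected record happened. Applied to a record named COLONOSCOPY, the same reading gives whether a colonoscopy was done. That is a different question from whether it reached the caecum.

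The subjects on whom the two answers differ are those whose colonoscopy was started but did not reach the caecum. They are the failures that this endpoint should count, and an occurrence flag would score them as successes. Completion is a declared secondary endpoint under the objective on colonoscopy quality indicators, and the section plans a country-adjusted CMH test and a difference in proportions with its 95% CI. All of these would then describe whether colonoscopy was performed.

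**Working it through.** The documents give no completion rate and no figure for this endpoint, so there is nothing to reproduce. The check compares text with code, followed by an illustration on assumed rates.

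**Does the SAP separate performed from completed?** Yes, in three places.

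- SAP 3.2.4 plans a flow chart that counts colonoscopies performed and colonoscopies completed.
- SAP 3.2.1.2.5 (Table 8) censors procedures that did not reach the caecum.
- SAP 3.2.1.2.6 leaves subjects whose caecum was not reached out of the examination-duration analysis.

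**What does the code select?** One record type (colonoscopy, Visit 2, ITT) and one variable. If PROCCUR is an occurrence flag, its Yes count in an arm is *d*, the number of colonoscopies done. The endpoint needs *c*, the number that reached the caecum, with *c* ≤ *d*. With *N* subjects per arm:

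- overstatement of the proportion in an arm = (*d* − *c*)/*N*
- error in the treatment difference = [(*d*₁ − *c*₁) − (*d*₂ − *c*₂)]/*N*

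The second expression is zero when equal numbers fail intubation in the two arms. When *d*₁ = *d*₂, it equals minus the whole true difference.

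**Illustration.** *N* = 125 is the planned number randomised per arm, assumed here to be the ITT number. The share with a colonoscopy (100%, or about 98%, taken as 122 of 125) and the caecal rates among those done are assumptions. Counts are rounded to whole subjects, with 112.5 taken as 112.

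| Done per arm | Assumed caecal rates | Caecum reached | True difference (÷125) | Difference from an occurrence flag |
|---|---|---|---|---|
| 125 | 97% v 97% | 121 v 121 | 0 | 0 |
| 125 | 97% v 90% | 121 v 112 | 9/125 = 7.2 points | 0 |
| 125 | 95% v 85% | 119 v 106 | 13/125 = 10.4 points | 0 |
| 122 | 97% v 97% | 118 v 118 | 0 | 0 |
| 122 | 97% v 90% | 118 v 110 | 8/125 = 6.4 points | 0 |
| 122 | 95% v 85% | 116 v 104 | 12/125 = 9.6 points | 0 |

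In the first row the difference is right, but completion would be reported as 125/125 = 100% where the true value is 121/125 = 96.8%. With 125 done in each arm the flag is constant, so there is nothing to test and the output would look odd. With 122 done in each arm the code would run and return a believable 122/125 = 97.6% in both arms.

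**The case against.** The strongest reply is that PROCCUR is undefined, so its meaning is inferred. Appendix 1 item 8 (rescue) is built in the same form as item 5 (completion), and the rescue code tabulates CMOCCUR. It could therefore be argued that in this SAP a variable ending in OCCUR simply holds the Appendix 1 Yes/No, and that PROCCUR holds item 5. This cannot be excluded: the code reads an analysis dataset, and SAP 3.2.10 says derived data follow Appendix 1. But the parallel does not settle it. For an enema, being given and being needed to achieve preparation amount to the same thing. For a colonoscopy, being done and reaching the caecum do not, and nothing in the SAP says that the caecum answer is stored in PROCCUR.

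Three further points stand and limit the concern.

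- SAP 3.2.1.2.5 reports by arm the numbers and percentages with caecal intubation and the numbers censored, with a Cox test. A difference lost from the completion table would still show there.
- SAP 4.3 requires outputs to be checked against the SAP and against each other, so a conflict between those two tables could be caught. Double programming, however, is specified only for the primary endpoint.
- SAP 3.1.5 makes all secondary tests descriptive.

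A reader might go further and infer that the trial would lose its only information on failed intubations, or that the code certainly measures the wrong endpoint. The documents support neither inference. The intubation table and the flow chart carry the same information, no passage makes completion the sole cover for failed intubations, and PROCCUR could have been filled correctly.

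**Conclusion.** The text and the code do not match as written. The definition is clear and consistent, but the code does not name the variable that carries it, and the natural reading of the variable it does name is a different quantity. On that reading, completion is overstated in each arm by the share of subjects whose colonoscopy was done but did not reach the caecum. Any difference between arms that arises from failed intubation is hidden.

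The size cannot be stated from the documents. It runs from no effect on the difference, when caecal rates are equal, to loss of the whole difference when they are not (6.4 to 10.4 points in the unequal cases assumed above). This rests on two assumptions: that PROCCUR means occurrence, and that colonoscopy is performed equally often in both arms.

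This is a minor point. It touches one descriptive secondary endpoint and leaves the primary analysis, sample size and alpha unchanged.

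**What to change.** In SAP 3.2.1.2.4, replace PROCCUR in the CMH table request with the Yes/No completion flag derived in Appendix 1 item 5, still crossed by COUNTRYC and TRTP. If PROCCUR was always meant to hold that derivation, say so in Appendix 1 instead.

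It would help to state the denominator in the same edit. The text speaks of procedures, while item 5 as worded would also give No to an ITT subject who had no colonoscopy. In the illustration with 122 done and 97% v 90%, the choice moves the difference only from 8/125 = 6.4 to 8/122 = 6.6 points.

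The cost is one variable name and one sentence. No new data are needed, because the caecum item is already in the eCRF.
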